
Project status

The team had originally planned to enroll 20,000 patients per arm, and 80,000 patients total. However, the study team decided to stop the study with just under 15,000 patients per arm due to logistical constraints.

Specifically, reaching the target sample size would have required us to enroll many patients who live far from existing Miller-Keystone donation sites and far from the Danville and Bloomsburg areas where Miller-Keystone often runs blood drives. Due to staffing shortages, it was not feasible to set up the additional blood drives that would have been required to enroll these patients and reach the original target sample size.

As of 4/25/2022, enrollment is complete with eligible patients that live near an existing Miller-Keystone donation site or near Danville or Bloomsburg, where Miller-Keystone ran blood drives for patients in the study. The final sample includes total of 59,093 patients.

The team has extracted primary-outcome data for the first group of participants enrolled. The data were extracted in order to set up a data pulling and sharing protocol with Miller-Keystone. However, these initial data have not yet been analyzed, and data for patients enrolled subsequently have not yet been extracted. Additionally, data collection for some participants is ongoing. We plan to extract the remaining primary outcome data all at once on or after 6/6/2022, 6 weeks following the final message send date (4/25/2022).

With the final sample size of at least 14,772 patients per arm, we will have 80% power to detect an increase in donation rates from 1% to 1.35% between any two study arms, a 35% difference, with a two-tailed alpha of .05. With our original planned sample size of 80,000 patients (~20,000 per arm), we would have had power to detect a smaller increase, from 1% to 1.3%.

Sample and randomization

The sample includes Geisinger patients who have a blood type recorded in their electronic health record, are age 18 or older, and do not have a low hemoglobin test result (<12.5) recorded in the 3 months before the patient list was extracted.

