Importantly, our messages are being sent on different dates in geographic regions (with some overlap), and blood donation patterns vary across the year. To control for variation in blood donation, we will attempt to determine standard donation rates across time, and to include this variable as a covariate in our analysis.

4. Time to donation

We will run regression models to test whether either intervention message influenced the timing (time elapsed since the message was sent) of donations.

5. Type of donation

We will test whether there are differences in donation type (particularly whole blood and

red blood cell donations) as a function of experimental group.

6. Demographics

We will run regression models to test for main effects of several demographic factors on donation behavior, along with interactions between these factors and message group. These demographic factors include binned age (18-24, 25-34, 35-44, 45-54, 65+), sex, race, ethnicity, line of insurance (as a proxy for socioeconomic status), and Charlson Comorbidity.

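### The age bins for the exploratory demographic models leave out ages 55 to 64, so eligible patients in that decade have no category

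*SAP*

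**What the plan says.** The last item under the SAP's additional exploratory analyses (6, Demographics) plans regression models to "test for main effects of several demographic factors on donation behavior, along with interactions between these factors and message group". Age enters these models as a categorical factor, given as "binned age (18-24, 25-34, 35-44, 45-54, 65" and over. That makes five bins, the last open at the top.

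The section on sample and randomization sets the age criterion. Patients with a recorded blood type qualify if they "are age 18 or older, and do not have a low hemoglobin test result" in the preceding three months. It gives no upper age limit. The project status section states: "The final sample includes total of 59,093 patients".

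The SAP nowhere excludes ages 55 to 64, assigns them to a neighbouring bin, or says how a patient without an age category is to be handled.

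**The concern.** A set of categories for a regression factor has to place every eligible patient in exactly one level. This set does not, because it skips a full decade in the middle of the adult range. A program written from the list has to do something with those patients, and the SAP does not say what. There are two likely outcomes:

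- **Age category set to missing.** A complete-case regression deletes these patients from every model that contains age, including the age-by-message interaction. If age is fitted together with sex, race, ethnicity, insurance and comorbidity, they are also lost from those estimates.
- **Bins built as separate 0/1 indicators.** A patient aged 55 to 64 scores zero on all of them and joins the reference level. With 18-24 as reference, for example, that level would mix the youngest adults with those near retirement age. Every age contrast and age-by-message interaction would then be measured against the mixture. No error or missing-data count would reveal it.

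In neither case would the analysis say whether the messages worked differently at ages 55 to 64. The choice would be made in programming, when it should be fixed in the plan before results are known.

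**Working it through.** **Plan's own figure.** The SAP gives no count or percentage for age. Its only design figure is the power statement: "With the final sample size of at least 14,772 patients per arm", "80% power to detect an increase in donation rates from 1% to 1.35% between any two study arms", "with a two-tailed alpha of .05". The usual formula for two proportions, with p̄ = (0.01 + 0.0135)/2 = 0.01175, gives

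n = [1.960·√(2 × 0.01175 × 0.98825) + 0.842·√(0.01 × 0.99 + 0.0135 × 0.9865)]² / 0.0035² ≈ 14,879 per arm.

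Power at 14,772 per arm is 79.7%. The stated 80% is thus reproduced to rounding. It contains no age term, so the gap in the bins does not affect it.

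**Coverage of the bins.** Each whole-number age from 18 to 110 was checked for membership in exactly one bin.

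| Age range | Listed bins containing it |
|---|---|
| 18–24, 25–34, 35–44, 45–54 | one each |
| 55–64 | none |
| 65 and over | one |

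The uncovered ages are exactly 55, 56, 57, 58, 59, 60, 61, 62, 63 and 64. No bins overlap, and there is no other gap from 18 upward. With a 55-64 bin added, the number of uncovered ages is zero.

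**How many patients.** The share aged 55 to 64 is not in the SAP, so a range of 10% to 20% is assumed. The SAP also leaves open which arms enter these models, so three denominators are shown. The two smaller ones use the stated minimum of 14,772 per arm.

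| Patients in the model | Total | 10% aged 55–64 | 20% aged 55–64 |
|---|---|---|---|
| All four groups | 59,093 | 5,909 | 11,819 |
| Three shortage groups (3 × 14,772) | 44,316 | 4,432 | 8,863 |
| Two message groups (2 × 14,772) | 29,544 | 2,954 | 5,909 |

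**How many events.** Per arm, 10% to 20% of 14,772 is 1,477 to 2,954 patients. At the 1% donation rate used in the power statement, that is about 15 to 30 donors per arm (1,477 × 0.01 = 14.8; 2,954 × 0.01 = 29.5). Donors are few in this study, so interaction tests can ill afford to lose or misplace them.

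**The case against.** The strongest reply is that this is an obvious slip in a list. Four consecutive bins are followed by a jump of exactly one decade, and an analyst who tabulated age would probably see the unclassified patients and repair it. The SAP does not say that anyone is to be deleted, so dropping out is the usual consequence of literal coding but not a certain one. The size rests on an assumed age share, and the largest count includes the no-shortage control group, which may not enter a model of message group. Loss from the other demographic estimates occurs only if all factors are fitted together, and the SAP does not say that they are. The bins appear only in the last exploratory item.

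Most of this stands as a limit on the consequences. Deletion is one of two likely outcomes, the counts are illustrative, and the reach is narrow. It does not remove the defect. The possible repairs also differ: a 55-64 bin may have been left out, or the last bin may have been meant to start at 55, and the two give different models. Relying on the analyst to notice means settling the categorisation during programming, and under indicator coding there may be nothing to notice.

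**Conclusion.** The concern holds. As written, the age factor has no category for ages 55 to 64, although these patients are eligible and no other text in the SAP covers them. This rests on the list and the age criterion alone and needs no assumption.

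The number affected does need one. At an assumed share of 10% to 20%, it is about 5,909 to 11,819 of all 59,093 patients, and proportionately fewer if only some groups enter the models. Whatever the share, literal coding gives no estimate of message effect for that decade. The damage is confined to the exploratory demographic models. Analyses 1 and 2 use only a binary message indicator, the secondary outcomes follow the same approach, and the power statement does not involve age. The list should be corrected, but it does not threaten the main conclusions.

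**What to change.** Change the age list in item 6 to 18-24, 25-34, 35-44, 45-54, 55-64 and 65 or over. This continues the ten-year pattern from 25 onward and is the most natural reading. The sponsor should confirm it, because a final bin starting at 55 is the other possible intention. It would also help to state how a patient with no recorded age is coded, so that no one enters the reference level by default.

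The cost is one line in the SAP. The age factor goes from five levels to six, which adds one main-effect term and, for each message-group contrast in the model, one interaction term. No data collection or design change is needed. According to the project status section, the first group's outcome data had been extracted but not analysed and the rest were still to be extracted, so at the date of the SAP the correction could be made without knowledge of results.
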